| AEs | adverse events |
| AI | artificial intelligence |
| ALT | alanine transaminase |
| ALP | alkaline phosphatase |
| AST | aspartate transaminase |
| ATC | anatomic therapeutic chemistry |
| BMI | body mass index |
| CBC | complete blood count |
| CAP | controlled attenuation parameter |
| CI | confidence interval |
| COVID-19 | Coronavirus disease 2019 |
| CRO | clinical research organization |
| C-SSRS | columbia-suicide severity rating scale |
| CTCAE | common terminology criteria for adverse events |
| CTX | carboxy-terminal collagen crosslinks |
| DILI | drug-induced liver injury |
| ECG | electrocardiogram |
| eCRF | electronic Case Report Form |
| eDISH | evaluation of drug induced serious hepatotoxicity |
| eGFR | estimated glomerular filtration rate |
| EOS | end of study |
| ET | early termination |
| FGF21 | fibroblast growth factor 21 |
| FIB-4 | fibrosis-4 score |
| FU | follow-up |
| GGT | gamma-glutamyl transferase |
| HbA1c | hemoglobin A1c |
| HDL-c | high density lipoprotein |
| HIV | human immunodeficiency virus |
| ICC | intraclass correlation coefficient |
| INR | international normalized ratio for prothrombin test |
| IP | investigational product |
| LDL-c | low density lipoprotein |
| LLOQ | lower limit of quantification |
| LS Mean | least-squares mean |
| MedDRA | medical dictionary for regulatory activities |
| MMRM | mixed-model repeated measures |
| MRI-PDFF | magnetic resonance imaging – proton density fat fraction |
| n | sample size |

| | |
|----------|---|
| NAFLD | nonalcoholic fatty liver disease |
| NAS | NAFLD activity score |
| NASH | nonalcoholic steatohepatitis |
| NASH CRN | NASH Clinical Research Network |
| non-HDL | non-high density lipoprotein |
| P1NP | n-terminal propeptide of type 1 collagen |
| PD | pharmacodynamics |
| PEG | polyethylene glycol |
| PK | pharmacokinetics |
| Pro-C3 | n-terminal propeptide of type iii collagen |
| PT | preferred term |
| QTcF | corrected QT interval by Fridericia |
| QW | weekly |
| SAEs | serious adverse events |
| SAP | statistical analysis plan |
| SC | subcutaneous |
| SD | standard deviation |
| SE | standard error |
| SMC | safety monitoring committee |
| SOC | system organ class |
| T2D | type 2 diabetes mellitus |
| TB | total bilirubin |
| TEAE | treatment-emergent adverse event |
| TSH | thyroid stimulating hormone |
| ULN | upper limit of normal |
| ULOQ | upper limit of quantification |
| VCTE | vibration-controlled transient elastography |
| WHO | world health organization |
| WOCBP | women of child-bearing potential |

1. Introduction

This statistical analysis plan (SAP) describes the statistical methods and procedures to be implemented in Part 2 of clinical study BIO89-100-002. This statistical analysis plan is based on study protocol BIO89-100-002 Version 5.0 dated 11 March 2021. If the data suggest then deviations from this plan will be considered. However, any deviations from the SAP must be substantiated by sound statistical rationale and documented in the final clinical study report.

2. Study Objectives

2.1. Primary Objectives

The primary objectives of Part 2 of the study are:

- To evaluate the safety and tolerability of subcutaneous (SC) injections of 27 mg BIO89-100, administered weekly for 20 weeks, in subjects with biopsy-proven NASH (NAFLD activity score (NAS) ≥ 4 , fibrosis stage F1 with high risk, F2 or F3).
- To characterize effect of BIO89-100 on liver histology

2.2. Secondary Objectives

The secondary objectives of Part 2 of the study are:

- To characterize biomarkers, pharmacodynamics (PD) profile and biological activity of BIO89-100
- To characterize effect of BIO89-100 on liver histology
- To characterize BIO89-100 pharmacokinetics (PK)

3. Study Overview

3.1. Study Design

Part 2 of study BIO89-100-002 is an open-label cohort (Cohort 7) in which BIO89-100 will be administered SC weekly at a single dose level (27 mg QW) to approximately 20 subjects with biopsy-proven NASH (NAS ≥ 4 , fibrosis stage F1 with high risk, F2 or F3), to evaluate effect on histological endpoints.

| Cohort | Dose Level ^a | Frequency and Route of Administration | Number of Subjects | |
|--------|-------------------------|---|--------------------|---------|
| | | | BIO89-100 | Placebo |
| 7 | 27 mg | QW, SC to abdomen (2 injections) Days 1, 8, 15, 22, 29, 36, 43, 50, 57, 64, 71, 78, 85, 92, 99, 106, 113, 120, 127, and 134. Total doses: 20 | 20 | NA |

^aThe actual doses will be $\pm 5\%$ the mg dose due to technical considerations related to drug withdrawal from the vials into the syringes for injection. This difference is considered negligible for subject exposure.

The study will include a Screening period, a Treatment period, and a Follow-up period. After signing informed consent, subjects will undergo screening assessments to determine eligibility over a period of up to 60 days.

For each subject in Part 2 (Cohort 7), the total duration of study participation will be up to 229 days (31.5 weeks), excluding the potential study interruption due to the Coronavirus disease 2019 (COVID-19) pandemic:

- Screening period: ≤60 days (8.5 weeks)
- Treatment period: 141 days (20 doses in 19 weeks)
- Follow-up period 28 days (4 weeks)

3.2. Study Activities

Please refer to the appendix for the schedule of activities and PK sample collection schedules:

- Appendix [12.1](#) Schedule of Activities for Part 2 (Cohort 7)
- Appendix [12.2](#) PK Sample Collection for Part 2 (Cohort 7)

3.3. Randomization Schedule and Blinding Procedures

Part 2 will be open-label with all subjects receiving the same dose (i.e., 27 mg SC QW) of BIO89-100.

3.4. Stratification Factors

There are no stratification factors for Part 2.

3.5. Sample Size and Power

For Part 2, no formal power calculations were used to determine the sample size in Cohort 7 and the number of subjects was chosen based on clinical experience with similar proof-of-concept histology studies and feasibility. This sample size accounts for an anticipated [REDACTED] of subjects who will not undergo the post-baseline liver biopsy (e.g., [REDACTED] to have paired liver biopsies). With a sample size of [REDACTED], the 95% confidence interval of the histological response rate would have a half-width no greater than [REDACTED] assuming the histological response [REDACTED]. The actual half-width will depend on the observed histological response rate [REDACTED].

3.6. Interim Analysis

No efficacy interim analysis is planned. Sponsor may perform administrative interim analyses to support objectives such as study planning and regulatory interactions.

3.7. Safety Monitoring Committee

Part 2 will not have a Safety Monitoring Committee (SMC) as described for Part 1 since there will be no dose escalation decisions to adjudicate. Part 2 safety data will be reviewed on an ongoing basis by the Sponsor and/or clinical research organization (CRO) Medical Monitors.

4. Study Endpoints

4.1. Primary Endpoints

Part 2 of this study has primary safety and primary efficacy endpoints, which are detailed in Sections 4.1.1 and 4.1.2, respectively.

4.1.1. Primary Safety Endpoints

The primary safety endpoints are:

- Subject incidence of treatment-emergent adverse events (TEAEs)
- Subject incidence of serious TEAEs

4.1.2. Primary Efficacy Endpoint

The primary efficacy endpoint is:

- At least a 2-point improvement in NAS with at least a 1-point improvement in ballooning or lobular inflammation, and no worsening of fibrosis

4.2. Secondary Endpoints

The secondary PD endpoints are:

Anthropometric measurements:

- Change from baseline and percent change from baseline in body weight over time

Laboratory parameters:

- Change from baseline and percent change from baseline in triglycerides over time
 - Change from baseline and percent change from baseline in triglycerides over time in subjects with baseline triglycerides ≥ 150 mg/dL
- Change from baseline and percent change from baseline in non-high density lipoprotein (non-HDL) cholesterol over time
- Change from baseline and percent change from baseline in high density lipoprotein (HDL-c) over time
 - Change from baseline and percent change from baseline in HDL-c over time in subjects with baseline HDL-c < 40 mg/dL for males and < 50 mg/dL for females
- Change from baseline and percent change from baseline in low density lipoprotein (LDL-c) over time
 - Change from baseline and percent change from baseline in LDL-c over time in subjects with baseline LDL-c ≥ 100 mg/dL
- Change from baseline and percent change from baseline in hemoglobin A1c (HbA1c) over time

Liver function tests:

- Change from baseline and percent change from baseline in alanine transaminase (ALT) over time
- Change from baseline and percent change from baseline in aspartate transaminase (AST) over time
- Change from baseline and percent change from baseline in n-terminal propeptide of type III collagen (Pro-C3) over time

Imaging measures:

- Change from baseline and percent change from baseline in magnetic resonance imaging – proton density fat fraction (MRI-PDFF)

Histology measures:

- Improvement of fibrosis ≥ 1 stage without worsening of NASH
- NASH resolution without worsening of fibrosis

PK measures:

- Trough concentration of BIO89-100

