4.3. Part 2 Eligibility Criteria

4.3.1. Part 2 Inclusion Criteria

Subjects are eligible to be included in the study only if all of the following criteria apply:

Age and Gender

1. Subjects must be 21 to 75 years of age inclusive, at the time of signing the informed consent form (ICF).
2. Male or female.

Type of Subject and Disease Characteristics

3. Increased metabolic risk; subjects must have at least 2 of the following:
 - a. Central obesity: Waist circumference of >102 cm for males, >88 cm for females, or body mass index (BMI) >30 kg/m². BMI should not exceed 50 kg/m²
 - b. Fasting plasma glucose ≥ 126 mg/dL or previously diagnosed T2DM
 - c. Increased fasting triglycerides (≥ 150 mg/dL) or on treatment for hypertriglyceridemia
 - d. Reduced fasting HDL cholesterol (<40 mg/dL for male and <50 mg/dL for female)
 - e. Hypertension or treatment of previously diagnosed hypertension

Only subjects meeting Criterion 3 should be further evaluated for participation. Subjects who do not initially meet Criterion 3 may be re-tested, based on investigator judgment.

4. Evidence of fibrosis – must meet at least one of the following criteria:
 - a. Fibroscan VCTE score ≥ 8.5 kPa at screening or within the last 3 months¹⁰ AND Aspartate aminotransferase (AST) > 20 U/L for males or > 17 U/L for females in the first screening measurement¹¹
 - b. A historical liver biopsy obtained more than 24 weeks and less than 2 years before Screening with Stage 1, 2 or 3 fibrosis.
5. Evidence of steatosis by Fibroscan and MRI-PDFF:
 - a. All subjects must complete a Fibroscan with CAP measurement. Fibroscan must be done with a subject-appropriate probe during screening; CAP score should be ≥ 280 dB/m at screening or within the last 3 months unless an MRI-PDFF $\geq 8\%$ within the last 12 months is available and the current CAP score is similar to or greater than CAP score when previous MRI-PDFF was done.

NOTE: If a Fibroscan model with CAP technology is not available, MRI-PDFF will be adequate to assess steatosis.
 - b. MRI-PDFF $\geq 8\%$ at screening (MRI must be completed no more than 35 days prior to baseline)
6. Biopsy-proven NASH in a liver biopsy obtained within 24 weeks of baseline with fibrosis stage F1, F2, or F3 and NAS ≥ 4 , with a score of at least 1 in each of steatosis, ballooning degeneration, and lobular inflammation.

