5.3.2. Study Baseline for Lipids

For lipids, the baseline will be determined as the average of all pre-dose measurements within 30 days prior to Study Day 1, e.g., measurements taken at $-29 \leq \text{Study Day} \leq 1$ (Pre-dose).

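### The Part 2 lipid subgroup endpoints select subjects on the same baseline that change is measured from, with no control arm, so part of the subgroup change is regression to the mean

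*SAP*

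**What the plan says.** SAP Part 2, section 4.2, nests three subgroup endpoints under the whole-cohort lipid endpoints:

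- Triglycerides: "Change from baseline and percent change from baseline in triglycerides over time in subjects with baseline triglycerides ≥ 150 mg/dL".
- HDL-c: change in "HDL-c over time in subjects with baseline HDL-c" below 40 mg/dL (men) or 50 mg/dL (women).
- LDL-c: "Change from baseline and percent change from baseline in LDL-c over time in subjects with baseline LDL-c ≥ 100 mg/dL".

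Section 5.3.2 gives the only lipid baseline: "the baseline will be determined as the average of all pre-dose measurements within 30 days prior to Study Day 1". No separate qualifying value is defined for subgroup membership.

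Section 3.3 describes one open-label dose group. Section 8.1.2 describes a repeated-measures model with the parameter's own baseline as covariate, no comparator and no multiplicity adjustment. It yields LS means with p-values and 95% confidence intervals. Section 8.4.3.1 applies that model to all lipid parameters. The visible text does not mention regression to the mean or an external comparison for these subgroups.

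**The concern.** A measured baseline is the subject's usual level plus error. Keeping only subjects whose measured baseline lies beyond a cut over-represents those whose error points that way. Later values do not carry that error, so the subgroup mean moves back toward normal without treatment: down for triglycerides and LDL-c, up for HDL-c. All three moves look like benefit.

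A placebo group would show the same drift and allow it to be subtracted, but Part 2 has none. Zero change is then not what would be expected of an inactive drug in these subgroups, and an estimate or interval read against zero overstates activity. The primary histology endpoint is not affected.

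**Working it through.** The plan states no effect size or SD for lipids, so there is no figure to reproduce.

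**Inputs from the documents.** Cuts of 150 mg/dL (triglycerides), 40/50 (HDL-c) and 100 (LDL-c); 20 subjects; averaged pre-dose baseline. Protocol Table 6 marks clinical laboratory tests in two screening columns and on Day 1, and Table 9 places lipids in that panel, so two or three samples (k) are likely.

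**Inputs assumed.** Triglyceride geometric mean 140 or 170 mg/dL; between-subject log SD 0.35; within-subject CV 20% to 30%; independent errors; no drug effect.

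**Mechanism in closed form.** On the log scale, with a baseline averaged over k log values:

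expected change = -(σ²/k) / s × λ(z), where σ² = ln(1 + CV²), s = √(0.35² + σ²/k), z = (ln 150 - ln GM)/s, and λ(z) is the standard normal density at z divided by the upper tail beyond z.

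For GM 140, CV 25%, k = 2:
- σ² = ln(1.0625) = 0.0606, so σ²/k = 0.0303
- s = √(0.1225 + 0.0303) = 0.391
- z = 0.0690/0.391 = 0.176, and λ = 0.914
- change = -(0.0303/0.391) × 0.914 = -0.071, a fall of about 6.8% in geometric mean with no drug effect.

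**Arithmetic scale, as planned (simulation).** Mean triglyceride change in the subgroup, mg/dL:

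| Baseline samples | Geometric mean | CV 20% | CV 25% | CV 30% |
|---|---|---|---|---|
| 2 | 140 | -7.1 | -10.5 | -14.2 |
| 2 | 170 | -4.7 | -7.1 | -9.8 |
| 3 | 140 | -4.9 | -7.3 | -9.8 |
| 3 | 170 | -3.1 | -4.8 | -6.6 |

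These shifts are 0.21 to 0.58 of a standard error at the implied subgroup size of 9 to 13.

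For HDL-c (single cut of 45, CV 7% to 10%) the shift is +0.3 to +0.8 mg/dL. With separate cuts by sex and other assumed means it reaches about +1.0. For LDL-c (CV 8% to 12%) it is -0.6 to -1.8 mg/dL.

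**Does the baseline covariate help?** No. In a single group, the least-squares mean at the subgroup's mean baseline equals the raw mean change. In one simulated triglyceride case both were -8.75 mg/dL.

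**Selecting on a sample left out of the baseline.** With independent errors, the mean mg/dL change falls to about 0 for all three lipids. If half the within-subject variance is slow and shared across the screening samples, -4.7 to -13.2 mg/dL remains for triglycerides, against -6.2 to -20.4 under the planned rule.

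**Percent change.** Dividing by a noisy baseline adds an upward bias of about CV²/k. With k = 2 this is 0.04/2 = 2.0%, 0.0625/2 = 3.1% and 0.09/2 = 4.5% for CVs of 20%, 25% and 30%. It is present in unselected subjects too. Under the planned rule it partly offsets the selection bias (net -0.7% to -5.2%); once selection is separated, it stands alone. A log-scale analysis removes it, provided the baseline samples are also averaged as logs. Taking the log of an arithmetic average instead leaves about -(σ²/2)(1 - 1/k), which at CV 25% and k = 2 is -(0.0606/2) × 0.5 = -0.015, or -1.5%.

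**The case against.** Several points on the other side stand.

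- **Averaging is already a mitigation.** The 5.3.2 baseline cuts the artefact by roughly half to two-thirds compared with a single reading. The figures above include it.
- **The size is modest.** A second set of assumptions puts the triglyceride artefact at 1% to 6% with two or three readings. Protocol 2.3.3 reports preliminary Part 1 triglyceride reductions of up to 28% overall and up to 49% in a high-baseline subgroup. A reader might infer that regression to the mean explains the subgroup results; the documents do not support that.
- **Subgroup p-values are not certain.** A reader might infer that the SAP commits to testing each subgroup against zero. Section 8.4.3.1 does not say that the model is run within subgroups, 8.1.2 refers to selected parameters, and some analysis text is redacted. The bias in the estimates does not depend on this.
- **Enrolment is a weak further route.** Inclusion criterion 3 lists triglycerides and HDL-c, and Protocol 4.3.1 adds: "Subjects who do not initially meet Criterion 3 may be re-tested, based on investigator judgment". A reader might infer that the whole-cohort lipid baseline is contaminated too. But any two of five items qualify a subject, treatment for hypertriglyceridaemia counts without a raised value, and a qualifying sample more than 30 days before Day 1 is already outside the baseline. This route is unquantified and does not justify changing the whole-cohort baseline.
- **Separate-sample selection is not a complete cure**, as the shared-variance result shows.

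**Conclusion.** The point holds in limited form. One averaged baseline selects the subgroup and anchors its change, nothing in the planned model corrects for this, and all three biases favour the drug. For triglycerides the artefact is about -3 to -14 mg/dL, at most about 0.6 of a standard error. For HDL-c and LDL-c it is too small to matter much. These sizes rest on assumed means, spread and within-subject CVs, on two or three baseline samples, and on independent errors. Shared error across screening would make the artefact larger.

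This is a matter of how three secondary subgroup results are read. It does not show that the drug has no lipid effect, nor that the whole-cohort lipid endpoints are invalid. It is worth correcting because the correction is cheap.

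**What to change.** In SAP Part 2:

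1. In 4.2, assign membership of the three subgroups from the first fasting screening lipid sample, whether or not the subject is later re-tested.
2. For these subgroup endpoints only, compute baseline from the remaining pre-dose samples, leaving that one out. Keep the 5.3.2 baseline for the whole cohort.
3. Analyse subgroup percent change on the log scale, averaging baseline samples as logs, and report geometric mean ratios.
4. Present the subgroups as descriptive, with estimates and intervals but no p-values against zero change. Show beside them the matching subgroup of Part 1 pooled placebo (19 subjects planned), selected and baselined by the same rule. This matters because step 2 removes only part of the bias if error persists across screening. The benchmark is imperfect: it is small, its population differs and its treatment period was shorter.

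**Cost.** SAP wording and some reprogramming; no new procedures. The subgroup baseline is slightly noisier. Footnote h to Table 6 names only ALT and AST for the Day -7 to -3 visit, so confirm that lipids are measured there; if not, the subgroup baseline may rest on Day 1 alone. About 10% to 30% of the triglyceride subgroup, under the assumptions used, would have an analysis baseline below 150 mg/dL. The endpoint wording should therefore refer to the screening value.

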4.3. Other Safety Endpoints

The other safety endpoints are:

- Subject incidence of TEAEs by severity
- Number of subjects who discontinued due to TEAEs
- Number of subjects who discontinued due to related TEAEs
- Change from baseline in vital signs
- Incidence and shifts of clinically significant vital signs
- Incidence of clinically significant physical examination findings
- Incidence and shifts of clinically significant electrocardiograms (ECG)
- Incidence and shifts of clinically significant laboratory abnormalities
- Change from baseline in safety laboratory evaluations including complete blood count (CBC), blood biochemistry, urinalysis and bone biomarkers (CTX and P1NP)

Immunogenicity measures:

- Incidence and characteristics of anti-drug antibodies (ADA) after dosing (e.g., titer and/or binding specificity, to the fibroblast growth factor 21 (FGF21) and polyethylene glycol (PEG) part of BIO89-100 and neutralizing immunogenicity)
- Impact/correlation of the presence of ADAs on serum BIO89-100 concentrations and clinical safety

4.4. Exploratory Endpoints

5. Definitions

5.1. Definition of Study Day

The day subjects receive their first dose of investigational product (IP) will be considered Study Day 1. Study day will be defined by the number of days from Study Day 1. If index date is prior to Study Day 1, study day will be defined as the index date minus the Study Day 1 date. If index date is on or after Study Day 1 date, the study day will be defined as index date minus the Study Day 1 date plus 1 day. If a subject did not receive IP, the study day will be set as missing.

For subjects with study interruptions due to COVID-19, post-interruption study day will be calculated as: (Index date) – (the date of Study Day 1) + 1 – (the interruption duration as defined in the study interruption CRF). Visits post-interruption due to COVID-19 will use this corrected study day for visit windowing.

5.2. Handling of Missing or Partial Dates

Date imputation will only be used for determining treatment-emergent status for adverse events or identifying concomitant medications. Actual data values as they appear in the database will be shown in the subject level listings.

5.2.1. Adverse Event Date Imputations

In cases of incomplete dates for adverse events, the missing components will be assumed as the most conservative values as possible. The imputation rules described below will attempt to conservatively capture AEs with missing onset dates as treatment-emergent, unless information of AE stop date/time was prior to first dose date, which would automatically disqualify the treatment-emergent status. The original values with no imputation applied will be presented in the data listings.

- If “day” is the only missing field, impute the “day” as the day of Study Day 1 date if the month and year of Study Day 1 are equal to the AE start month and year; otherwise, impute the “day” as the first day of the AE start month.
- If “day” and “month” are missing, impute the “day” and “month” as the day and month of the first dose date if “year” is the same as the year of Study Day 1; otherwise, impute January 1 of the non-missing year.
- Missing time will not be imputed. If “time” is missing and the start date or imputed start date is the same as the first dose date, then the time is assumed to be after the dose time so that the event will be classified as treatment-emergent.
- If the start date is completely missing:
 - and from the end date (either complete or partial date) it can be deduced to be prior to the first dose date, then the AE will not be assigned as a TEAE.
 - and from the end date (either complete or partial date) it cannot be deduced to be prior to the first dose date, then the AE will be assigned as a TEAE.
 - Start dates that are completely missing will not be imputed.

